3.5 Study Duration

This study will consist of an inclusion visit, i.e. Visit 1 (the subject will be randomised and start treatment that day) and a 4- to 9- day dosing period. In this study, subjects are expected to take the study treatment with a minimum of 24 sachets to be taken in 4 days to 5 days and with a maximum of 48 sachets to be taken in 8 or 9 days. Visit 2 will be on Day 5 or Day 6 and Visit 3 will be on Day 9 or Day 10.

The subject's participation in the study will be considered to have ended when the subject will have recovered from diarrhoea, defined as one formed stool followed by a nonwatery stool and when the last follow-up visit is performed.

The study will be considered to have started when the first subject has been enrolled/ provided signed informed consent.

3.6 Stopping Rules and Discontinuation Criteria

There are no formal rules for early termination of this study. During the conduct of the study, serious adverse events (SAEs) will be reviewed (see Section 8.1.4) as they are reported from the study centre to identify safety concerns. The study may be terminated by the sponsor at any time.

A subject may discontinue participation in the study at any time for any reason (for example, lack of efficacy, withdrawal of consent, AE). The investigator and/or sponsor can withdraw a subject from the study at any time for any reason (for example, protocol violation or deviation as defined in Section 12.1.2, noncompliance with the protocol conditions or AE).

3.7 Investigational Medicinal Product Preparation Storage and Accountability

3.7.1 *Investigational Medicinal Product Storage and Security*

The investigator, or an approved representative (for example, pharmacist), will ensure that all IMP and any other study related material is stored in a secured area, under recommended temperature monitored storage conditions, in accordance with applicable regulatory requirements.

3.7.2 *Investigational Medicinal Product Preparation*

The investigator, or an approved representative (for example, pharmacist), will ensure that all IMP is dispensed by qualified staff members.

3.7.3 *Investigational Medicinal Product Accountability*

All IMP and any other study related material is to be accounted for on the IMP accountability log provided by the sponsor. It is essential that all used and unused supplies are retained for verification (by the sponsor or sponsor's representative). The investigator should ensure adequate records are maintained in the IMP accountability log.

The destruction of used and unused IMP (active or placebo) should be carried out only after any discrepancies have been investigated and satisfactorily explained and the reconciliation has been accepted. The study treatment will be destroyed either at site or in the interim storage facility or in a dedicated company that has agreement

for the destruction of IMP. In case it is not possible to destroy the IMP in the country, the IMP will be sent back to the sponsor for destruction.

3.8 Maintenance of Randomisation and Blinding

Two sets of individual sealed code break envelopes will be prepared by the sponsor's randomisation manager to enable emergency code break procedures for individual subjects without compromising the blind of the study. One set will be provided to the investigational site and one set will be provided to the Central Department of Pharmacovigilance at the sponsor.

Code break envelopes will only be opened in cases of medical emergency when treatment is dependent on knowledge of the IMP received. In the event of an SAE or unexpected AE, which requires the identification of the study treatment group, the investigator should first contact the Pharmacovigilance Representative outlined in the protocol. The investigator should then review the case status and all pertinent information with the representative from the Central Department of Pharmacovigilance who will consult with the Therapeutic Area Drug Safety physician prior to any code break.

Once it has been determined that knowledge of the treatment code is necessary, the investigator will ascertain the subject's identification number and randomisation number, and then break the blind for the subject concerned. The investigator will then sign date and provide reason for the code break on the Emergency Code break form, and on the code break envelope. Moreover, the investigator is allowed to unblind the trial randomisation code in case of emergency endangering a subject without prior consultation with the sponsor.

Monitors should routinely check the integrity of the envelopes that are stored at the study site. They must collect envelopes from the study site prior to study close out and ensure that they are all intact. If envelope(s) have been opened at the site or by the sponsor's representative, the monitor must ensure a written explanation is clearly documented (opener's name, dated signature and reason for opening) on the visit status page of the eCRF.

Confirmation of the integrity of all code break envelopes at study completion must be documented in the Trial master file (TMF). All sets of the sealed individual subject envelopes must be kept in the TMF in the co-ordinating office at study completion for proof of integrity.

3.9 Source Data Recorded on the Case Report Form

Data will be collected in the eCRF in compliance with FDA 21 Code of Federal Regulations (CFR) Part 11. As required by GCP, the sponsor assigned monitor will verify, by direct reference to the source documents, that the data required by the protocol are accurately reported on the eCRF.

The source documents must, as a minimum, contain a statement that the subject is included in a clinical study, the date that informed consent was obtained prior to participation in the study, the identity of the study, diagnosis and eligibility criteria, visit dates (with subject status), IMP administration, and any AEs and associated concomitant medication.

As required by ICH GCP Section 6.4.9, if some items are recorded directly on the eCRF and are considered as source data, the identification of these data must be documented and agreed between the investigator and the sponsor.

Definition for source data and source documents are given below:

-
- **Source Data:** All original records and certified copies of original records of clinical findings, observations, or other activities necessary for the reconstruction and evaluation of the study. Source data are contained in source documents (original records or certified copies).
 - **Source Documents:** Original documents, data and records (for example, hospital records, clinical and office charts, laboratory notes, memoranda, subjects' diaries or evaluation checklists, pharmacy dispensing records, recorded data from automated instruments, copies or transcriptions certified after verification as being accurate copies, microfiches, photographic negatives, microfilm or magnetic media, x rays, subject files, and records kept at the pharmacy, at the laboratories and at medicotechnical departments involved in the clinical study).

The subject must have consented to their medical records being viewed by the sponsor's authorised personnel, and by local, and possibly foreign, Competent Authorities (CAs). This information is included in the informed consent.

4 SELECTION AND WITHDRAWAL OF SUBJECTS

4.1 Inclusion Criteria

All subjects must fulfil all of following criteria to be included in the study:

- (1) Provision of written informed consent prior to any study related procedures,
- (2) male or female subject (outpatient) legally considered as an adult (age of majority). In Czech Republic the upper limit of age will be 70 years inclusive.
- (3) subject has a diagnosis of acute diarrhoea presumed of infectious origin, defined as:
 - the passage of 3 or more unformed loose or watery stools (rated according to the Bristol scale) per day without associated alarm symptoms*
 - having started within 48 hours before Visit 1 (first study drug intake time).
- (4) subject has, usually, normal bowel habits, (Rome III criteria) **, i.e. at least 3 stools per week and no more than 3 stools per day,
- (5) subject must be willing and able to comply with study restrictions and willing to return to the clinic for the follow up evaluation(s) as specified in the protocol.

*Symptoms considered as alarm symptoms are identified in the exclusion criteria (1)

4.2 Exclusion Criteria

Subjects will not be included in the study if they meet:

- **Exclusion criteria related to the acute diarrhoea episode:**

- (1) At least one of the following alarm symptoms*
 - bloody diarrhoea*,
 - pus in the stools*,
 - fever $\geq 38.0^{\circ}\text{C}$ *,
 - moderate or severe dehydration according to World Health Organisation (WHO) definition, requiring intravenous (IV) rehydration*,
 - repeated vomiting*
 - persistent abdominal pain*

*These symptoms are considered as alarm symptoms

- (2) other episode of acute watery diarrhoea within the previous 30 days,
- (3) persistent diarrhoea, defined as acutely starting episode of diarrhoea lasting more than 14 days,
- (4) history of chronic diarrhoea (Rome III criteria); i.e. 3 or more loose or watery stools per day for at least 12 weeks, consecutive or not, in the preceding 12 months,
- (5) traveller's diarrhoea defined as a diarrhoeal episode due to contamination experienced by subjects having travelled in at risk countries, or coming from abroad and experiencing locally an acute diarrhoea episode, occurring usually within the first 2 weeks of the stay in a foreign environment.

- **Exclusion criteria related to drugs:**
 - (6) Diarrhoea suspected to be induced by drug for example:
 - antibiotic therapy, including Clostridium difficile-induced diarrhoea, within 1 week before entry in the study,
 - laxative agent
 - thyroid hormone (at a nonstabilised dosing),
 - colchicine intake, etc... (See [Appendix 1](#))
 - (7) anti-diarrhoeal agent intake during the last month,
 - (8) any subject requiring repeated intake of a drug with a narrow therapeutic margin (for example, digoxin, theophylline, etc...) (See [Appendix 2](#)),
 - (9) history of hypersensitivity to diosmectite or its excipients or placebo components,
 - (10) subject likely to require treatment during the study with drugs that are not permitted by the study protocol (for example, antibiotic agent, anti-diarrhoeal agent, antiemetic drug, antispasmodic drug),
 - (11) use of any investigational medication within the last 30 days before entering this study,
 - (12) subject who previously entered in a clinical study within the past 30 days.

- **Other digestive exclusion criteria:**
 - (13) History of gastric or intestinal resection, vagotomy,
 - (14) known digestive malabsorption disease, including coeliac disease
 - (15) known lactose intolerance,
 - (16) any suspicion of abdominal surgery need,
 - (17) known inflammatory bowel disease.
- **Other exclusion criteria:**
 - (18) Known Human immunodeficiency virus (HIV) positive status,
 - (19) known or suspected immunosuppression,
 - (20) known severe renal or hepatic insufficiency,
 - (21) Uncontrolled diabetes of all types and non insulin dependant diabetes during first 6 months of medical treatment and other known endocrine disease,
 - (22) history of, or known current, problems with alcohol abuse and/or known drug addiction (cocaine, heroin, hashish...),
 - (23) previous enrolment in this study,
 - (24) any mental condition rendering the subject unable to understand the nature, scope and possible consequences of the study, and/or evidence of an uncooperative attitude,
 - (25) Pregnant or lactating women.

4.3 Subject Withdrawal Criteria and Procedures

In accordance with the Declaration of Helsinki (in accordance with the applicable country's acceptance), each subject is free to withdraw from the study at any time and for any reason. The investigator and/or subject will be asked to perform/attend a final visit at any time in case of withdrawal, whatever the reason. The investigator also has the right to withdraw a subject from the study in the event of concurrent illness, AEs, or other reasons concerning the health or well-being of the subject, or in the case of lack of cooperation. In addition, a subject may be withdrawn from the

study as described in Section 3.6. Should a subject decide to withdraw from the study after administration of IMP, or should the investigator decide to withdraw the subject, all efforts will be made to complete and report the observations up to the time of withdrawal as thoroughly as possible. A complete final evaluation at the time of the subject's withdrawal should be made (see Section 5.2.4) and an explanation given of why the subject is withdrawing or being withdrawn from the study.

The reason for and date of withdrawal from the study must be recorded on the eCRF. If a subject withdraws consent, every attempt will be made to determine the reason. If the reason for withdrawal is an AE or a clinically significant laboratory test abnormality, monitoring will continue until the event has resolved or stabilised, until the subject is referred to the care of a local health care professional, or until a determination of a cause unrelated to the IMP or study procedure is made. The specific AE or test result(s) must be recorded on the eCRF. All evaluations should be performed, according to the protocol, on the last day the subject receives IMP, or as soon as possible thereafter.

5 STUDY PROCEDURES

5.1 Study Schedule

Table 2 Study Schedule

| Visit (Day) | Visit 1 | Visit 2 (Day 5 or 6) | Visit 3 (Day 9 or 10) | Early withdrawal |
|---|---------|----------------------|-----------------------|------------------|
| Informed Consent | X | | | |
| Demographic Data | X | | | |
| History of current acute diarrhoea episode | X | | | |
| Medical and surgical history | X | | | |
| Prior and concomitant medications for acute diarrhoea episode | X | X | X | X |
| Physical Examination | X | X | X | X |
| Vital Signs | X | X | X | X |
| Eligibility criteria | X | | | |
| Randomisation | X | | | |
| Study drug administration | X[a] | X[b] | X[c] | X |
| Patient diary (DEB) delivery/verification/collection | X | X | X | X |
| Visit status | X | X | X | X |
| Concomitant/surgical procedures | | X | X | X |
| Adverse events | X | X | X[d] | X |
| Prior and Concomitant Medications/ Non drug Therapies excluding those taken for acute diarrhoea episode | X[e] | X | X | X |
| Faecal sampling and results for microbiology analysis | X[f] | X[g] | | |
| Faecal virological results | | X | | |

a The first treatment must be taken during Visit 1. It will be taken in the morning, mid-day or in the evening depending on the time of Visit 1. The morning intake can be until 11am, the mid-day intake until 6pm, the evening intake can be after 6pm.

b a minimum of 24 sachets should be taken within 4 or 5 days

c a maximum of 48 sachets should be taken within 8 or 9 days

d reported by the subject until 7 days after the end of the study treatment

[figure not shown]
e taken within 30 days preceding Visit 1

f A fresh stool will be collected as soon as possible after inclusion

g faecal results will be recorded at Visit 2

A summary of the study design is presented in [Figure 1](#).

Figure 1 Study Design

* DSP = Placebo

** DS = Diosmectite

*** Only for subjects who did not recover by Visit 2

A summary of the chart for the Bristol scale is presented in [Table 3](#).

Table 3 Chart for Bristol scale

| Bristol Scale | Subject Inclusion | Subject Recovery (first formed stool followed by a nonwatery stool) | |
|---------------|-----------------------------------|--|-----------------|
| | | First formed stool | Nonwatery stool |
| Type | Diarrhoea (Loose or watery stool) | | |
| 1 | | X | X |
| 2 | | X | X |
| 3 | | X | X |
| 4 | | X | X |
| 5 | | | X |
| 6 | X | | |
| 7 | X | | |

5.2 Study Visits

5.2.1 *Visit 1 (Procedures for Enrolment, Day 1)*

A signed and dated informed consent form will be obtained before screening procedures. Evaluations obtained as part of routine medical care and performed during the screening period may be used in place of the study specific evaluations. Subjects will acknowledge and agree to the possible use of this information for the study by giving informed consent.

After informed consent is obtained, at enrolment, subjects will be allocated a subject number. All enrolled subjects must be identifiable throughout the study. The investigator will maintain a list of subject numbers and names to enable records to be found at a later date if required.

Enrolment (Visit 1) will take place within 48 hours after onset of diarrhoea. The following assessments will be performed:

- eligibility check (inclusion/exclusion criteria),
- demographic data (date of birth/age and sex will be collected according to individual country requirements),
- medical and surgical history, including ongoing medical conditions
- history of the current acute diarrhoea episode including:
 - date and time (hours, minutes) of first watery stool,
 - number of stools including number of watery stools and for each 12h period during the last 24 hours,
 - presence of other associated symptoms for the last 24 hours: nausea, vomiting, abdominal pain, anal irritation.
- physical examination,
- vital signs (blood pressure and heart rate in sitting position, respiratory rate, body temperature, body height and weight),
- one faecal sampling for microbiological examination to be collected as soon as possible after inclusion,
- prior and concomitant medications/non-drug therapies (excluding those taken for acute diarrhoea episode) taken within 30 days preceding the enrolment/inclusion visit,
- prior and concomitant medications for acute diarrhoea episode

Following confirmation of eligibility for the study, subjects will be given a randomisation/treatment allocation number and allocated to receive either diosmectite or placebo as specified in Section 6.1.

- collection of AEs,
- study treatment unit will be delivered to the subject according to the randomisation procedure,
- visit Status will be recorded
- start of treatment at the centre: time of first intake of study treatment (data to be recorded in the eCRF).
- the DEB and information for use will be delivered to the subject. Refer to Section 5.2.5 for details to be recorded in DEB

Next visit will be performed after at least 24 sachets have been taken (i.e. 4 or 5 days after the first visit (i.e. Day 5 or Day 6)).

Under no circumstances will subjects be enrolled more than once. Each investigator will also maintain a record of all subjects enrolled into the study (i.e. who signed the informed consent form). Records up to the time of premature termination should be completed. In the event that the subject was not receiving IMP, the primary reason will be recorded.

5.2.2 *Visit 2 (follow-up or End of study, Day 5 or Day 6)*

The following procedures will be performed:

- Adverse events will be reported by subject since the last visit and will be collected.
- The Investigator will check in the DEB if clinical data were appropriately recorded and if the study drug was appropriately used.
- Any change in the concomitant medication and/or surgical procedures since Visit 1 will be checked and recorded in the eCRF.
- A physical examination and body weight measurement will be performed.
- Vital signs (blood pressure, heart rate in sitting position, respiratory rate, body temperature and body weight) will be checked.
- Faecal microbiological results will be recorded
- Visit Status will be recorded

In case of recovery, the study treatment will be stopped. A last visit (Visit 3) will be planned at Day 9 or 10 for subjects who did not recover by Visit 2

5.2.3 *Visit 3 (End of study if patient is not recovered at Visit 2, Day 9 or Day 10)*

- Adverse events will be reported by subjects since the last visit and will be collected until 7 days after the last treatment intake.
- Any change in the concomitant medication and/or surgical procedures since Visit 2 will be checked and recorded in the DEB.
- A physical examination and body weight measurement will be performed.
- Vital signs (blood pressure, heart rate in sitting position, respiratory rate body temperature and body weight) will be checked.
- The Investigator will check in the DEB if clinical data were appropriately recorded and if the study drug was appropriately used. A copy of the DEB will be kept in the subject's file and the original will be sent to the Sponsor (Data Management).
- Visit Status will be recorded

Treatments units with used and unused sachets will be kept by the investigator.

5.2.4 *Early Withdrawal Visit*

- Adverse events will be reported by subjects since the last visit and will be collected until 7 days after the last treatment intake.
- Any change in the concomitant medication and/or surgical procedures since the previous visit will be checked and recorded in the DEB.
- A physical examination and body weight measurement will be performed.
- Vital signs (blood pressure, heart rate in sitting position, respiratory rate, body temperature and body weight) will be checked.

- The Investigator will check in the DEB if clinical data were appropriately recorded and if the study drug was appropriately used. A copy of the DEB will be kept in the subject's file and the original will be sent to the Sponsor (Data Management).

In case of either:

- impaired general health condition
- and/or moderate or severe dehydration
- and/or fever above 38°C
- and/or pus or blood in the stool
- and /or positive microbiological finding for *Entamoeba histolytica* or *Giardia/Lamblia* or *Shigella* in stool, the subject will be withdrawn from the study and an effective rehydration therapy and/or an anti-parasitic or antibiotic treatment will be immediately given accordingly.

If the subject is discontinued from the study (i.e., ceases participation in the study prior to completion of the protocol), the reason will be recorded in the eCRF. Withdrawal due to AEs (see Section 8.1.2) should be distinguished from other conditions for withdrawal. The investigator will record the reason for study discontinuation, provide or arrange for appropriate follow up (if required) for such subjects, and document the course of the subject's condition.

In all cases, the investigator must ensure the subject receives appropriate medical treatment (i.e. need for IV rehydration, and/or antiparasitic, and/or antibiotic therapy) and follow up to determine the final outcome if the period of the trial is over.

5.2.5 *Diary Evaluation Booklet (DEB)*

The primary endpoints will be recorded in the DEB. The subject will be asked to record in the DEB each day, including at Day 1, the following data until the next visit: date, time of onset and consistency of stools (according to the Bristol scale; see [Appendix 3](#), presence of symptoms such as nausea, vomiting, abdominal pain, anal irritation, and study drug consumption (number of sachets taken each day). See also Section 7.4.

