6.2 Concomitant Medication/Therapy

Any prior or concomitant therapy or medication given to a subject within 30 days before IMP administration or during IMP administration will be indicated on the eCRF. Dose and generic name or tradename will be indicated.

The following concomitant medications are not permitted during this study:

- Antibiotics

- Anti-diarrheal agents
- Antiemetic drugs
- Antispasmodic drugs

All forbidden concomitant medication are listed in [Appendix 1](#) and [Appendix 2](#).

The following hydration and dietary advices will be provided if the subject does not have signs of dehydration:

- have frequent water intake and small meals, throughout the day:
 - intake mixed low fiber foods such as eggs (white mainly), white meats, beef, fish, cheese, white rice, potatoes, white bread, pasta, semolina, tapioca, cassava,...
- avoid canned fruit juices, beverages with sorbitol, alcohol, coffee, tea, or other caffeinated beverages, fatty foods, fried meats or fish, high fibre-rich foods such as oily seeds (e.g. almonds, peanuts, etc.), fruits, beans, lentils, chickpeas, raw vegetables.

In case of mild dehydration, food intake could be started after correction of dehydration, using Oral Rehydration Salts (ORS) therapy according to World Health Organisation (WHO)/United Nations Children's Fund (UNICEF) recommendation (Clinical management of acute diarrhoea WHO/UNICEF joint statement 2004).

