7.3 Microbiological Tests

A fresh stool will be collected as soon as possible after inclusion for microbiological laboratory testing (for virology, bacteriology and parasitology testing) in order to determine the microbiological status of this acute diarrhoea episode , i.e. the absence/presence of the following faecal pathogens:

Virology testing

- rotavirus,
- adenovirus,
- norovirus,

Bacteriology and parasitology testing

- enteropathogenic and Enterotoxigenic Escherichia Coli (E. coli),
- staphylococcus aureus,
- shigella,
- salmonella,
- campylobacter,
- yersinia enterocolitica,
- amoebiasis (entamoeba histolytica),
- giardia / lamblia.

Details of the methodology and technical specifications will be provided in the laboratory manual located in the Investigator Site File and in the TMF.

Laboratory test results provided by the lab will be recorded in the laboratory results section of the eCRF by the investigator at Visit 2.

7.4 **Methods and Timing of Assessing, Recording, and Analysing Efficacy Data**

The subject will be asked to complete, each day from Day 1 (day of Visit 1) to the end of the treatment visit (Visit 2 (Day 5 or Day 6) or Visit 3 (Day 8 or Day 9)), the DEB with the following information:

- Stools:
 - date and time to onset,
 - consistency rated as either watery, loose, formed or hard (according to the Bristol scale; see [Appendix 3](#)),
- Presence or not of an episode for each 12-hour period:
 - nausea,
 - vomiting,
 - abdominal pain
 - anal irritation.
- abdominal pain intensity (rated with a 5-point ordinal scale: 0 = absent, 1= mild, 2 =moderate, 3 = severe, 4= very severe)
- Study drug consumption (number of sachets per day)

Methods for assessing efficacy data are described above in Section 7.1 and Section 7.2. Timing of efficacy assessments are discussed in Section 5. Procedures for recording efficacy data are discussed in Section 14.1, and methods of analysis are discussed in Section 10.4.5.

8 **ASSESSMENT OF SAFETY**

8.1 **Adverse Events**

Adverse events will be monitored from the time that the subject gives informed consent and throughout the study until 7 days after the end of study treatment (see Section 3.5 for a definition of the study duration) and will be elicited by direct, non-leading questioning or by spontaneous reports. Further details for AE reporting can be found in Section 8.1.2.

8.1.1 ***Definition of an Adverse Event***

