In the event of multiple incidences of the same primary system organ class /preferred term being reported by the same subject, the subject will be counted once for that primary system organ class/preferred term.

These summaries will be produced on the safety population.

3.2.8 *Subject compliance*

Data collected from both “Study Treatment Administration (on site)” eCRF section and “Study drug intake” part of the DEB will be presented in individual listings with information such as date of intake, time of intake when taken on site and number of sachets taken by the subject. Listings will be ordered by treatment group, subject and visit, for all subjects of the Safety set.

Study drug exposure (days) will be summarized on the safety population.

Summary statistics on number of sachets taken during the mandatory period (from Day1 to Day4/Day5), until recovery and until end of study will be displayed by treatment group.

Compliance will be expressed in percentage as the total sachets taken based on the expected total sachets to be taken and will be calculated during the mandatory treatment period for all subjects, until the recovery for subjects with recovery and until the end of study for subjects with no recovery (see section 3.2.12). Compliance will be categorized as < 80% (Under compliance), 80-120% (Compliance) and > 120% (Over compliance) and will be summarized in percentage and in class overall, on the safety population.

3.2.9 *Prior and concomitant therapies*

Two types of medications will be analysed:

- **General medications:** using the information retrieved from the “Prior and Concomitant Medications (Excluding current acute diarrhoea episode)” eCRF section.
- **Medications related to current diarrhoea episode:** using the information retrieved from the “Prior and Concomitant Medications for the current acute diarrhoea episode” eCRF page.

Prior medications are defined as the medications taken within 30 days preceding visit 1 and stopped prior to the first study drug intake.

Concomitant medications are defined as medications that have been taken during the treatment period regardless the start or stop date. For any partial date, if it is not clear when the medication started or ended but shows a possibility that it has been taken during the treatment period then it will be considered as a concomitant medication.

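### Protocol 5.2.3 and 5.2.4 send concomitant-medication and procedure changes to the diary, against 5.2.2, 6.2 and 14.1, while the SAP takes medication only from eCRF pages

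*Protocol*

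**What the plan says.** **Visit instructions (Protocol 5.2).** Three parallel bullets name two recording places:

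- Visit 2 (5.2.2): "Any change in the concomitant medication and/or surgical procedures since Visit 1 will be checked and recorded in the eCRF".
- Visit 3 (5.2.3): "Any change in the concomitant medication and/or surgical procedures since Visit 2 will be checked and recorded in the DEB".
- Early withdrawal (5.2.4): "Any change in the concomitant medication and/or surgical procedures since the previous visit will be checked and recorded in the DEB".

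**General rules.** Protocol 6.2 says that any therapy or medication given in the 30 days before or "during IMP administration will be indicated on the eCRF". Protocol 14.1 requires data on protocol procedures and safety to be entered on the CRF/eCRF. Table 2 schedules both medication items and surgical procedures at Visit 3 and at early withdrawal, without naming a recording place.

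**Diary content.** Protocol 5.2.5 and 7.4 and SAP 1.3.2.1 describe the DEB. Between them they list stool times and consistency, symptoms, abdominal pain intensity and sachets taken. None lists medication or procedures.

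**Analysis source.** SAP 3.2.9 takes general medication from one eCRF section and episode-related medication from the eCRF page titled "Prior and Concomitant Medications for the current acute diarrhoea episode". It names no diary source. SAP 3.2.8, on compliance, names both an eCRF section and a part of the DEB.

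**The concern.** The instruction specific to the visit and the source used for analysis point to different places. Staff working through Visit 3 or a withdrawal visit would naturally follow 5.2.3 or 5.2.4. If they write a medication change in the diary and nowhere else, the tables in SAP 3.2.9 will not contain it.

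The subjects concerned are those still unwell at Visit 2 and those who withdraw. It is reasonable to expect the classes prohibited by 6.2 (antibiotics, anti-diarrhoeals, antiemetics, antispasmodics) to be used more in these subjects than in those who recover early, although the documents give no usage rates.

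Two outputs are exposed. Concomitant medication usage is a stated safety evaluation (Protocol 3.2.3, SAP 3.1.3). The PP set depends on major deviations settled at the blind data review (Protocol 10.1.2, SAP 2.1.3), and a prohibited drug noted only in a diary could be missed there. If diosmectite works as planned, more placebo subjects reach Visit 3, so any shortfall in capture would not be balanced between arms.

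**Working it through.** The plan states no figure on this point, so there is none to reproduce. The check is a comparison of texts, followed by a rough count of the subjects covered.

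**Step 1. Recording place by provision**

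| Provision | Covers | Place |
|---|---|---|
| Protocol 5.2.2 | medication and procedure changes since Visit 1 | eCRF |
| Protocol 5.2.3 | medication and procedure changes since Visit 2 | DEB |
| Protocol 5.2.4 | medication and procedure changes since the previous visit | DEB |
| Protocol 6.2 | medication or therapy, 30 days before and during IMP | eCRF |
| Protocol 14.1 | protocol-procedure and safety data in general | CRF/eCRF |
| SAP 3.2.9 | source for medication tables | eCRF only |

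Sections 5.2.3 and 5.2.4 stand alone against the rest.

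**Step 2. What the conflicting text reaches**

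- At Visit 3 it covers only changes since Visit 2, because 5.2.2 already sends earlier changes to the eCRF.
- At early withdrawal it covers changes since the last visit. For a subject who leaves before Visit 2, that is the whole period on treatment.
- Procedures are less protected than medication. Section 6.2 does not mention surgical procedures, so only 14.1 sends them to the eCRF.

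**Step 3. Is there a stated route from diary to eCRF?** SAP 3.2.3.3 plans a check of DEB data before unblinding, with its focus on stool dates, times and consistencies. Protocol 3.9 has the monitor verify the eCRF against source documents, and diaries are among these. Neither is a stated reconciliation of medication notes in diaries.

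**Step 4. Number of subjects covered (scale only)**

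Inputs: medians of 55 h and 70 h, 427 subjects per arm and at most 5% premature withdrawal (Protocol 10.2); Visit 2 at 4 or 5 days after Visit 1, that is 96 or 120 h (Protocol 5.2.1). Assumption not in the documents: exponential recovery, so the share unrecovered at time t is 0.5^(t/median).

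| t | Diosmectite | Placebo | Total of 854 |
|---|---|---|---|
| 96 h | 0.5^(96/55) = 0.298; × 427 = 127 | 0.5^(96/70) = 0.387; × 427 = 165 | 292 (34%) |
| 120 h | 0.5^(120/55) = 0.220; × 427 = 94 | 0.5^(120/70) = 0.305; × 427 = 130 | 224 (26%) |

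The placebo share is higher by 8.8 points at 96 h (38.65 − 29.82) and by 8.4 points at 120 h (30.48 − 22.04). Premature withdrawals number at most 0.05 × 854 = 42.7, about 43. They may overlap with the unrecovered and should not simply be added.

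**The case against.** A reader might infer that medication data are lost for all unrecovered and withdrawn subjects. The documents do not support that, for these reasons:

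- Section 6.2 makes no exception for Visit 3, and its scope largely matches what SAP 3.2.9 tabulates: medication in the 30 days before Visit 1 and medication during treatment. A site that follows 6.2 enters the data correctly.
- Treatment first given after IMP has stopped falls outside the SAP's definitions of prior and concomitant medication wherever it is written down, so the DEB wording does not remove it from those tables.
- A diary note is retained. The original goes to Data Management, a copy stays in the subject's file, and diaries are source documents under Protocol 3.9.
- The booklet itself is not in the documents, so it cannot be said that it has no space for medication. The content lists describe mainly what the subject records each day, whereas the disputed bullets describe a check at a visit.
- No text says that PP exclusions rest only on the medication pages. Protocol 12.1.2 has sites record violations on the eCRF separately, and exclusions pass through the blind data review.
- Only the ITT primary analysis is confirmatory (SAP 3.1.4), and its censoring rules (SAP 3.2.12) use no medication data.

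All of this stands, and it limits the point to a risk of incomplete capture. It does not remove the contradiction. The general rules say one thing and the visit-level instruction, given twice, says another, with no stated step to reconcile the two.

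**Conclusion.** The text is wrong as written and should be corrected, but the consequence is modest. Protocol 5.2.3 and 5.2.4 contradict 5.2.2, 6.2 and 14.1 and direct data to a place that SAP 3.2.9 does not read. What is at risk is the completeness of the medication and procedure summaries, and the detection of prohibited medication when the supportive PP set is fixed. The confirmatory ITT result is not affected.

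Under the exponential assumption, the Visit 3 instruction would apply to about 22–30% of diosmectite and 31–39% of placebo subjects, and the withdrawal instruction to at most about 43 subjects. It would be a mistake to read these counts as subjects with missing data. The documents give neither a rate of medication use nor a rate of failed transcription, so the actual shortfall cannot be estimated.

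**What to change.** 1. In Protocol 5.2.3 and 5.2.4, replace DEB by eCRF in the medication and procedure bullet, so that both agree with 5.2.2 and 6.2. This is one word in each section, with a short note to sites.
2. Before the blind data review, check the diaries of Visit 3 and early-withdrawal subjects for notes of medication or procedures, and confirm that each is in the eCRF before PP exclusions are fixed. The original diaries already go to Data Management, so the cost is one targeted check.

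The second step matters more in practice: the SAP is dated 15 July 2019 and the study was planned to end in September 2019, so many of these visits will already have taken place. It should be done while treatment is still blinded, so that decisions on PP membership cannot be influenced by knowledge of the arm. SAP 3.2.9 needs no change, because its tables will include the entries once they are transcribed.
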